#### 9.14.3.6 PSA Measures Change from Baseline

Total PSA, PSA velocity, and PSADT levels will be summarized descriptively at each timepoint including a change from baseline. Boxplots showing the mean, median, Q1, Q3, and outliers for each PSA measure will be presented for each timepoint to investigate PSA over time.

Additional summaries of total PSA, PSA velocity, and PSADT levels will be presented for the following subgroups:

- Participants who received salvage focal therapy
- Participants who were TP for the primary analysis at the participant-level
- Participants who were FP for the primary analysis at the participant-level
- Participants who were TN for the primary analysis at the participant-level

All PSA, PSA velocity, and PSADT levels will be listed.

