- Assessment of PSA levels: PSA will be assessed in all participants at 90 days ± 15 days and if the participant is returning to the study site for further follow-up imaging, at 180 days ± 15 days post Day 0. If radiation therapy or other salvage focal therapy (e.g., cryotherapy) is initiated during the study (as long as no concomitant androgendeprivation therapy [ADT] is given), PSA levels must be monitored every 4 weeks from the initiation of the therapy. Prostate specific antigen response (defined as total PSA decline by ≥50% from baseline) must be confirmed by a second value within 4 weeks.

Central Review of Scans: The ⁶⁴Cu-SAR-bisPSMA PET/CT scans will be interpreted by an appropriately qualified local Investigator and three independent, blinded, central readers. Each reader will be required to evaluate the PET/CT scans individually for the presence of pathological ⁶⁴Cu-SAR-bisPSMA uptake in the prostate bed/gland, pelvic lymph nodes, extra pelvic lymph nodes, visceral/soft tissue and bone.

Expert Panel Composite Reference Standard: The ⁶⁴Cu-SAR-bisPSMA PET/CT findings will be assessed against a composite Reference Standard. The composite Reference Standard will be determined by an independent, blinded, central expert panel and may consist of histopathology, conventional imaging modalities that are routinely used in the diagnosis and staging of PC and PSA levels. The Investigator will be required to submit all relevant clinical evidence available for the participant to enable the assessment of the Reference Standard. The expert panel will determine the composite Reference Standard without knowledge of the ⁶⁴Cu-SAR-bisPSMA PET/CT results.

To assess the impact of ⁶⁴Cu-SAR-bisPSMA PET/CT on disease management, the treating physician will be required to fill out a Pre-SAR-bisPSMA and a Post-SAR-bisPSMA Disease Management Form to provide information on the treatment strategy of the participant before and after the information from the local read of the ⁶⁴Cu-SAR-bisPSMA PET/CT scan(s) becomes available.

See Figure 1 for the overall study design schema. Details on study procedures for each visit are described in Table 5 and Section 8.

Figure 1 Overall Study Design

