² Visit 6 is only applicable to participants who were deemed negative or equivocal for PC recurrence based on the Visit 5 follow-up conventional imaging (as per the central expert panel's interpretation).

³ Informed consent must be documented before any study-specific screening procedure is performed and may be obtained more than 28 days before the ⁶⁴Cu-SAR-bisPSMA administration.

⁴ Demographic data include: year of birth, race, ethnicity. Baseline disease characteristics include: initial diagnosis stage (per American Joint Committee on Cancer), initial Gleason score, initial diagnosis stage (T, N and M staging), pathology results, date of biochemical recurrence, relevant symptom history including, gastrointestinal, genitourinary and musculoskeletal.

⁵ Medical history will include evaluation of: relevant past or present diseases or disorders, and relevant surgical history. Medication history within 14 days before signing informed consent should be collected.

⁶ Physical examination includes assessment of: general appearance, cardiovascular system, respiratory system, and nervous system if vertebral involvement.

⁷ ECOG Scale is used by the Investigator to determine the score (0 to 5) that best represents the participants' activity status.

⁸ Vital signs include: body temperature, respiratory rate, heart rate and systolic and diastolic blood pressure.

⁹ Post-dose vital signs to be completed prior to the ⁶⁴Cu-SAR-bisPSMA PET/CT.

¹⁰ Post-dose ECG to be performed at 30 minutes (±10 minutes) post ⁶⁴Cu-SAR-bisPSMA administration.

¹¹ Hematology: hemoglobin, hematocrit, red blood cell count, WBC, platelet count, differential WBC (neutrophils, eosinophils, basophils, lymphocytes, and monocytes), absolute neutrophil count, and absolute lymphocyte count.

¹² Biochemistry (pre-prandial): albumin, total protein, blood glucose, sodium, potassium, blood urea nitrogen, creatinine, calcium, uric acid, AST, ALT, total bilirubin, alkaline phosphatase.

¹⁴ Urinalysis to include determination of protein, glucose and leukocytes (dipstick test).

¹⁵ If radiation or other salvage focal therapy is initiated during the study, PSA levels will be monitored independent of the study visit schedule at every 4 weeks (± 2 days) from the initiation of the therapy. PSA response (defined as total PSA decline by $\geq 50\%$ from baseline) must be confirmed by a second value within 4 weeks.

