8.1.4 Follow-Up

8.1.4.1 Day 90 (Day 90 ± 15 days, Visit 5)

This visit is to take place 90 days (\pm 15 days) after the ⁶⁴Cu-SAR-bisPSMA administration. All participants must complete this visit, regardless of the ⁶⁴Cu-SAR-bisPSMA PET/CT results.

Participants who based on the central expert panel's interpretation of the follow-up conventional imaging completed during Visit 5 are deemed:

- **negative or equivocal for PC recurrence** must continue to Visit 6.
- **positive for PC recurrence** no further study visits are required.

Assessments to be completed:

- Record Any Prostate Cancer Treatments (Refer to Section 7.1.4)
- Total PSA (Refer to Section 7.5.3)
- Follow-up Conventional Imaging (Refer to Section 7.3.3)
- Record Any Additional Imaging/Histopathology (Refer to Section 7.3.3 and 7.4)

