8.1.4.2 Day 180 (Day 180 ± 15 days, Visit 6)

This visit is to take place 180 days (\pm 15 days) after the ⁶⁴Cu-SAR-bisPSMA administration.

Only participants who were deemed negative or equivocal for PC recurrence based on the follow-up conventional imaging (as per the central expert panel's interpretation) completed during Visit 5 must complete Visit 6.

If the participant is not returning to Visit 6, but additional imaging/histopathology was acquired within 180 days (\pm 15 days) of Day 0, the relevant details must be recorded on the eCRF and information submitted to the central reading center.

Assessments to be completed:

- Record Any Prostate Cancer Treatments (Refer to Section 7.1.4)
- Total PSA (Refer to Section 7.5.3)
- Follow-up Conventional Imaging (Refer to Section 7.3.3)
- Record Any Additional Imaging/Histopathology (Refer to Section 7.3.3 and 7.4)

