10.4.5.3 Exploratory Efficacy Analyses

The exploratory efficacy endpoints include the following:

- Proportion of participants with any change in intended PC treatment due to either the Day 0 or Day 1 scan;
- Composite CDR, PPV and DR of the Day 0 and Day 1 scan;

- CDR, participant- and region-level PPV and DR of the Day 0 and/or Day 1 scan as a function of baseline variables;
- Relationship between PET-positivity (biodistribution measures such as SUVs and lesion-to-background ratio), versus true/false positivity and as a function of lesion location and size;
- Difference in the number of lesions detected per participant on the Day 0 versus the Day 1 scan;
- Lesion-level overall agreement rate on the Day 0 and Day 1 scans, on the Day 0 and reference scans, and on the Day 1 and reference scans;
- PSA over time and change from baseline;
- PSA velocity and PSA doubling time (PSADT) at the end of the study and at baseline.

Binary exploratory endpoints will be summarized with points estimates and corresponding 2-sided 95% exact binomial CIs based on the FAS.

Difference in the number of lesions detected per participant on the Day 0 versus the Day 1 scan will be summarized descriptively and compared using a paired *t*-test. Other exploratory endpoints including PSA value at each scheduled time point and change from baseline, PSA velocity, and PSADT will be summarized using descriptive statistics.

Descriptive statistics, graphical methods, and statistical modeling as appropriate may be used to explore the relationship between PET-positivity (biodistribution measures such as SUVs and lesion-to-background ratio) and true/false positivity.

In addition, CDR, PPV and DR will also be assessed as a function of the following baseline variables:

- PSA at baseline prior to the scan (<0.5, 0.5 <1.0, 1.0 <2.0, 2.0 <5.0, ≥5);
- PSADT;
- PSA velocity;
- Testosterone at baseline;
- SUV mean and max;
- Lesion-to-background ratio;
- Initial Treatment Received.

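### The PSA-over-time summaries set all men at baseline and Day 90 beside an imaging-selected group at Day 180

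*SAP*

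**What the plan says.** **Collection.** Protocol 3.1 says that "PSA will be assessed in all participants at 90 days" (within a 15-day window), and then, "if the participant is returning to the study site for further follow-up imaging, at 180 days". Protocol 8.1.4.2 defines who returns: "Only participants who were deemed negative or equivocal for PC recurrence based on the" Visit 5 follow-up imaging, as interpreted by the central expert panel, must complete Visit 6. For men read as positive at Visit 5, Protocol 8.1.4.1 says that "no further study visits are required".

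There is one exception. For men who start radiation or other salvage focal therapy, a footnote to Protocol Table 5 says that "PSA levels will be monitored independent of the study visit schedule at every 4 weeks". SAP 7.6 lists these values among the on-study PSA measurements.

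**Analysis.** Protocol 10.4.5.3 lists "PSA over time and change from baseline" as an exploratory endpoint. SAP 9.14.3.6 implements it: "Total PSA, PSA velocity, and PSADT levels will be summarized descriptively at each timepoint including a change from baseline". It adds that boxplots of each PSA measure "will be presented for each timepoint to investigate PSA over time". Further summaries follow for men who received salvage focal therapy and for true positive (TP), false positive (FP) and true negative (TN) participants. SAP 7.3 uses observed values without imputation unless stated otherwise. SAP 9.14.3.6 names no set of men common to all timepoints and no split by Visit 5 imaging status.

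**The concern.** Whether a man has a scheduled Day 180 PSA is decided by his Day 90 imaging. This is a design rule, not chance dropout. Side-by-side boxplots offered as PSA over time will be read as a trend, but the last box holds a different set of men from the first two.

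If imaging tends to turn positive at higher PSA, the men with higher PSA leave before the last box. The displayed trend is then flatter than the trend in any fixed group, and a reader might conclude that PSA settled after Day 90 when only the membership changed. The same applies to a comparison of the Day 90 change from baseline (all men) with the Day 180 change (Visit 6 men).

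**Working it through.** The plan gives no figure on this point to reproduce. The check traces the schedule against the analysis and then illustrates the size.

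**1. Who is in each column of total PSA**

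| Timepoint | Scheduled PSA | Source |
|---|---|---|
| Screening | all men | Protocol Table 5 |
| Day 90 | all men | Protocol 3.1, 8.1.4.1 |
| Day 180 | men negative or equivocal at Visit 5 | Protocol 3.1, 8.1.4.2 |

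With about 50 men planned, and 20%, 40% or 60% positive at Day 90 (assumed), the scheduled Day 180 column holds 50 × 0.8 = 40, 50 × 0.6 = 30 or 50 × 0.4 = 20 men.

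**2. Which measures are affected**

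- *Total PSA levels:* affected, because the columns are summarised over different men.
- *Change from baseline:* SAP 7.1.1 computes it within each man, so each Day 180 change is valid for that man. Only the comparison of the Day 90 summary with the Day 180 summary mixes groups.
- *Post-baseline PSADT and velocity:* SAP 7.6 gives one post-baseline value per man, anchored on the last on-study PSA (or the last before radiation). They do not form a Day 90/Day 180 series.

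**3. Which subgroups are affected**

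- *TP:* affected most. Men verified by Visit 5 imaging leave the schedule; men verified by histopathology or by PSA response may remain.
- *FP:* affected in part. A man leaves if Visit 5 imaging is positive only where it does not match a PET-positive subregion (Protocol 7.5.2).
- *TN:* not affected. TN requires a negative Reference Standard (Protocol 7.5.2, SAP 7.8), so a man read as positive at Visit 5 would not be TN.

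**4. Size: simple model**

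All inputs are assumptions, since the documents give no PSA distribution, no Day 90 positivity rate and no link between PSA and imaging. Baseline PSA is log-normal with median 1.0 ng/mL and log-SD 1. Every man has a doubling time of 9 months. There is no therapy. The odds of positive Day 90 imaging are multiplied by a fixed odds ratio (OR) per PSA doubling.

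Growth alone gives medians of 2^(3/9) = 1.26 at Day 90 and 2^(6/9) = 1.59 at Day 180. Selection multiplies the Day 180 median by a factor *f*, the ratio of the Visit 6 men's median to the median of all men. The display turns flat or falls when *f* is at or below 1.26/1.59 = 0.79.

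| Positive at Day 90 | OR 0.67 | OR 1 | OR 1.5 | OR 2 | OR 3 |
|---|---|---|---|---|---|
| 20%: *f* | 1.11 | 1.00 | 0.90 | 0.85 | 0.81 |
| 20%: Day 180 median | 1.76 | 1.59 | 1.42 | 1.34 | 1.29 |
| 40%: *f* | 1.24 | 1.00 | 0.81 | 0.72 | 0.65 |
| 40%: Day 180 median | 1.97 | 1.59 | 1.27 | 1.14 | 1.04 |
| 60%: *f* | 1.38 | 1.00 | 0.72 | 0.61 | 0.52 |
| 60%: Day 180 median | 2.19 | 1.59 | 1.14 | 0.97 | 0.83 |

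For example, at 40% positive and OR 2, 0.72 × 1.59 = 1.14. The display reads 1.00, 1.26, 1.14 although every man's PSA rises.

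**5. Size: doubling times that vary between men**

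Here the log-SD of baseline PSA is 1.1, the median doubling time is 9 months (log-SD 0.6 in the repeat run), 25% to 42% are positive and the OR is 1.25 to 2. Medians in all men are 1.00 at baseline, about 1.3 at Day 90 and about 1.7 at Day 180 if everyone were drawn. The Visit 6 men show about 1.13 to 1.55. At 42% positive the Day 180 median is 1.30 for OR 1.5 (flat) and 1.13 for OR 2 (falling; 1.14 in the repeat run). In that last case the same Visit 6 men followed throughout read 0.67, 0.88, 1.14, a steady rise. Median change from baseline at Day 180 is 0.39 to 0.54 in the Visit 6 men, against 0.61 if all were drawn.

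**The case against.** **Day 180 PSA is not confined to Visit 5 negatives.** A man positive at Visit 5 who receives salvage focal therapy has PSA every 4 weeks, so he can have a value near Day 180. This stands: the selection rule governs scheduled values only. It does not cure the problem. SAP 9.14.3.6 does not say which timepoint those values enter. The windows in SAP 7.9 are written for reference datapoints, which under SAP 7.7 include PSA response, and do not clearly cover every PSA draw. If the values do enter, the column mixes untreated imaging-negative men with post-therapy values.

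**The direction is not stated.** A reader might infer that the documents say the Day 180 group has lower PSA. They do not. Protocol 2.1 does note that imaging often fails to localise recurrence, especially when PSA is low, which makes the direction reasonable. On-study salvage therapy could alter it.

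**The size is assumed.** This stands. The 42% used above equals the assumed CDR in the sample size section, which counts true positives by any level of evidence; it is not a Day 90 imaging rate. The model also leaves out therapy.

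**Much is already visible.** SAP 7.2 reports n for continuous variables, SAP Appendix 1 footnotes the Visit 6 restriction, and all PSA values are listed. A reader would see n fall, but would not see which men left or what the trend is in those who stayed.

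**The stakes are low.** The analysis is exploratory and descriptive, with no formal hypothesis test. This stands and limits the weight of the point.

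**Conclusion.** The point holds for total PSA levels across timepoints and for setting the Day 90 change beside the Day 180 change. By design, the scheduled Day 180 values come from men selected on Visit 5 imaging, and the SAP provides no summary in a fixed group.

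Three stronger readings are not supported. The trend does not necessarily flatten or reverse: under the section 5 assumptions (25% to 42% positive, OR 1.25 to 2 per doubling) the Day 180 median runs from about 1.13 to 1.55 against about 1.3 at Day 90, and the flat or falling results reported are at 42% positive with OR 1.5 or 2. At OR 1 there is no distortion, and below 1 it runs the other way. The subgroups are not all distorted alike: the effect is mainly in TP, partly in FP and absent in TN. Within-man change and post-baseline PSADT and velocity are not invalidated.

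This is a correction to an exploratory presentation. CDR and PPV do not depend on it.

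**What to change.** In SAP 9.14.3.6:

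- Show n at each timepoint in the tables and on the boxplots.
- Add total PSA at baseline, Day 90 and Day 180 in the same men, namely those with a Day 180 value, in the overall, TP and FP tables and boxplots. The TN summary needs no change on this account.
- Split baseline and Day 90 total PSA by Visit 5 imaging status (positive; negative or equivocal).
- State which analysis visit the 4-weekly PSA values after salvage therapy enter, and show them separately from scheduled Visit 6 values.
- Label the scheduled Day 180 column as Visit 6 attendees (negative or equivocal at Visit 5). That label is correct only once the salvage-therapy values are kept apart.

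The cost is SAP wording, one extra table and smaller numbers in the matched summary. No new data are needed.

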7.5.2 Assessment of Reference Standard against the ⁶⁴Cu-SAR-bisPSMA PET/CT Results

For the assessment of the Reference Standard against the ⁶⁴Cu-SAR-bisPSMA PET/CT, region-level matching will be used for histopathology, subregion-level matching for imaging and participant-level matching for PSA response to radiation or other salvage focal therapy (refer to Section 7.5.1). Matching of the Reference Standard against the ⁶⁴Cu-SAR-bisPSMA PET/CT results will be completed via statistical programming.

Assessment of **region-level** Reference Standard against the ⁶⁴Cu-SAR-bisPSMA PET/CT results:

- Histopathology: A region that is ⁶⁴Cu-SAR-bisPSMA PET-positive (i.e., includes at least one unequivocal PET-positive lesion) and Reference Standard positive, will be assigned as true positive (TP) for the region-level status.
- Imaging: A subregion that is ⁶⁴Cu-SAR-bisPSMA PET-positive (i.e., includes at least one unequivocal PET-positive lesion) and Reference Standard positive (i.e., includes at least one unequivocal lesion detected on conventional imaging in that subregion), will be assigned as TP. A region that includes at least one TP subregion will be assigned as TP for the region-level status.
- A region that is ⁶⁴Cu-SAR-bisPSMA PET-positive (i.e., includes at least one unequivocal PET-positive lesion) and is Reference Standard negative based on at least 1 evaluable timepoint, will be assigned as false positive (FP) for the region-level status.
- A region that is ⁶⁴Cu-SAR-bisPSMA PET-negative (i.e., no unequivocal PET-positive lesion or only equivocal lesion(s) detected within the subregions) and Reference Standard negative, will be assigned as true negative (TN) for the region-level status.
- A region that has either non-evaluable ⁶⁴Cu-SAR-bisPSMA result for a specific timepoint or has a non-evaluable or inconclusive Reference Standard will not be assigned for that timepoint.

Assessment of **participant-level** Reference Standard against the ⁶⁴Cu-SAR-bisPSMA PET/CT results:

- A participant with at least one TP region AND/OR at least one unequivocal ⁶⁴Cu-SARbisPSMA PET-positive lesion and confirmed PSA response to radiation or other salvage focal therapy, will be assigned as TP for the participant-level status.
- A participant with at least one unequivocal ⁶⁴Cu-SAR-bisPSMA PET-positive lesion who does not meet the above criteria to be deemed TP, will be assigned as FP for the participant-level status.

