## 7.6 Calculation of PSA Doubling Time and PSA Velocity

The following values of PSA are collecting for this study:

- PSA at Initial Diagnosis
- Nadir PSA after initial definitive treatment
- Most Recent PSA prior to screening #1 and #2
- Screening PSA
- PSA taken during the study at day 90 and 180 (if appliable) or after start of salvage focal therapy (can vary)

PSA doubling time (PSADT) and PSA velocity will be calculated at baseline and during the study and require different definitions. PSA at initial diagnosis will not be used for any calculations of PSA velocity or PSADT.

For calculation of PSADT and PSA velocity at **Baseline**, which will be calculated for all participants:

- PSA Velocity = Slope of the line of best fit using all available data within 12 months prior to screening as well as screening value (excluding at initial diagnosis).
- PSADT = ln(2) / ((ln(PSA value at screening) ln(oldest PSA value within 12 months prior to screening)) / (# of months from oldest PSA value within 12 months prior to PSA at screening))

September 4, 2024 CONFIDENTIAL Page 18 of 46

For calculation of PSADT and PSA velocity for on-study measurements, only the last measure of PSA taken during the study will be used. The following calculations will be done for PSA measurements **Post-Baseline**:

- PSA Velocity = Slope of the line of best fit using all available data on-study, including screening value.
  - o If the participant initiated radiation therapy on-study, the last PSA value is instead the last PSA value PRIOR to initiating radiation therapy.
- PSADT = ln(2) / ((ln(Last on-study PSA value) ln(PSA at screening)) / (# of months from last on-study PSA value to PSA at screening))
  - o If the participant initiated radiation therapy on-study, the last PSA value is instead the last PSA value PRIOR to initiating radiation therapy.
- If a participant has no post-screening value prior to initiation of radiation therapy, they will be excluded from post-baseline calculations of PSADT and PSA velocity.

For the calculation of the line of best fit for PSA Velocity, the following equations will be used for each participant, where  $x_i$  is the date of the measurement in months from screening (screening is x = 0) for each value,  $y_i$  is the PSA value, and n is the total number of datapoints for the participant for that calculation:

$$\overline{X} = \frac{\sum_{i=1}^{n} x_i}{n} \quad \overline{Y} = \frac{\sum_{i=1}^{n} y_i}{n}$$

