## • Non-evaluable:

o A region that has either non-evaluable (NE) Cu-SAR-bisPSMA PET/CT results for a specific timepoint (Day 0 or Day 1) or has a non-evaluable or inconclusive Reference Standard will not be assigned for that timepoint.

Assessments of **Participant-Level** Reference Standard against the Cu-SAR-bisPSMA PET/CT results:

• True Positive:

September 4, 2024 CONFIDENTIAL Page 22 of 46

- A participant with at least one TP region and/or at least one unequivocal Cu-SAR-bisPSMA positive lesion in any region and a confirmed PSA response to radiation or other salvage focal therapy.
  - Confirmed PSA response following radiation or other salvage focal therapy (as long as no concomitant ADT is given) = total PSA decline ≥50% from baseline, confirmed by a 2nd value within 4 weeks per Prostate Cancer Working Group 3 criteria.

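### Total PSA change is summarised for TP and FP men although PSA response is itself a route to TP, so part of any difference is built in or reflects treatment

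*SAP*

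**What the plan says.** SAP 9.14.3.6 states that "Total PSA, PSA velocity, and PSADT levels will be summarized descriptively at each timepoint including a change from baseline". It continues: "Additional summaries of total PSA, PSA velocity, and PSADT levels will be presented for the following subgroups". The subgroups are men given salvage focal therapy, "Participants who were TP for the primary analysis at the participant-level", and the matching participant-level FP and TN men. SAP 7.1.1 defines change from baseline as the value minus the baseline value, so it is absolute.

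The TP rule in SAP 7.8 has two routes joined by and/or: at least one TP region, or a PET-"positive lesion in any region and a confirmed PSA response to radiation or other salvage focal therapy". Protocol 7.5.2 has the same rule ("confirmed PSA response to radiation or other salvage focal therapy, will be assigned as TP for the participant-level status"). SAP 7.8 defines the response as "total PSA decline ≥50% from baseline", confirmed by a second value within four weeks and without concomitant ADT. FP is a PET-positive man with an evaluable Reference Standard who does not meet the TP criteria.

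For post-baseline velocity and doubling time, SAP 7.6 says that after on-study radiation "the last PSA value is instead the last PSA value PRIOR to initiating radiation therapy". Men with no such value are excluded. No rule of this kind is given for total PSA, and the rule does not mention other salvage focal therapy.

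**The concern.** For some men the tabulated variable also assigns the subgroup. A PET-positive man with a confirmed PSA response goes to TP and cannot be FP. A treated PET-positive man with no response, no TP region and an evaluable reference stays in FP. Total PSA is then summarised by these groups with post-therapy values included.

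Treatment adds a second layer. Focal therapy is permitted after Visit 4 (protocol 6.3), and the post-scan management plan rests on the local read of the same scans (protocol 7.5.3). PSA change may therefore reflect treatment even in men who are TP by histology or imaging.

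At stake is interpretation. PSA falling in TP men and rising in FP men could be read as outside support for the scan classification when part of the pattern follows from the definitions.

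**Working it through.** **Plan figures.** The documents state no figure for this table. The planning figures supply group sizes only. The stated power for CDR reproduces: with n = 40, the smallest count whose exact 95% lower bound exceeds 20% is 14, and P(X ≥ 14 | 0.42) = 0.855, against a stated value above 85%. Expected TP men: 40 × 0.42 = 16.8, about 17. Expected PET-positive men: 40 × 0.65 = 26.

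**Tracing the definitions.**
- Confirmed responder, PET-positive, no TP region: TP by the second route. His fall of at least 50% is in the TP total PSA data if the qualifying value falls at a tabulated timepoint.
- The same man cannot be FP, so the share of confirmed responders in FP is 0% by definition.
- TN men are PET-negative and cannot enter TP by this route. The built-in part therefore lies mainly in TP versus FP.
- Velocity and doubling time are protected after radiation. After other salvage focal therapy they are not, and a smaller version of the problem remains.

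**Simple illustration (assumptions).** Suppose k of 17 TP men qualify by PSA alone with exactly a 50% fall, the others do not change, and all share one baseline B. The mean absolute change is −0.5 × B × k/17:
- k = 2: −5.9% of B
- k = 4: −11.8% of B
- k = 8: −23.5% of B

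**Mean and median (assumptions, relative scale).** Put the PSA-route men at −60% and the rest at +30%. With 3 of 17, the mean is (14 × 30 − 3 × 60)/17 = +14.1%. With 5 of 17, it is (12 × 30 − 5 × 60)/17 = +3.5%. The median is +30% in both cases. The SAP reports medians and quartiles as well as means.

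**Simulation (assumptions).** 400,000 PET-positive men were simulated. The ratio of follow-up to baseline PSA has median 1.2 (log SD 0.4) if untreated and 0.6 (log SD 0.6) if treated. TP by histology or imaging is independent of treatment and PSA. Response is a ratio of 0.5 or less, with no confirmation step. Entries are percent change, TP / FP.

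| Treated | TP by histology or imaging | Share of TP by PSA only | Mean | Median | Mean, PSA route removed |
|---|---|---|---|---|---|
| 10% | 30% | 8.1% | 17.1 / 27.6 | 10.3 / 17.6 | 24.3 / 24.1 |
| 10% | 50% | 3.6% | 20.8 / 28.0 | 12.6 / 17.7 | 24.0 / 24.5 |
| 25% | 30% | 18.1% | 0.9 / 23.9 | −6.9 / 13.4 | 15.6 / 15.5 |
| 25% | 50% | 8.8% | 8.3 / 23.9 | 1.2 / 13.6 | 15.4 / 15.3 |
| 50% | 30% | 30.6% | −19.4 / 16.6 | −38.9 / 4.7 | 1.0 / 1.1 |
| 50% | 50% | 16.0% | −9.7 / 16.3 | −22.0 / 4.5 | 1.0 / 0.8 |

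The definition alone can separate the groups, in medians as well as means when individual changes are spread out. Independence was assumed, so the table isolates the mechanism and does not estimate its size in this trial. It is also on a relative scale, whereas the SAP's change is absolute.

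**The case against.** A reader might infer that the SAP tests TP against FP, or offers this table as validation of the scan. It does neither. SAP 9.14.3.6 is descriptive, SAP 4.1 plans no formal hypothesis testing, and where the SAP intends a comparison, as in 9.14.3.3, it says so. That objection stands and limits the point to how the table will be read.

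A reader might also infer that non-response makes a man FP. It does not: FP also needs an evaluable reference and no TP region.

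Few men may be affected. PSA response is the third and last evidence level in protocol 7.5.1, and Day 90 conventional imaging is required for everyone. Post-therapy PSA is checked every four weeks, independent of the visit schedule, so a qualifying fall need not show in full at Day 90 or Day 180. These limits stand, although the and/or wording of the TP rule is looser than the hierarchy and leaves the number uncertain.

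Finally, the dependence can be traced. The section already has a salvage focal therapy subgroup and lists all PSA values, SAP 9.9 lists treatments with dates, and SAP 9.13 summarises and lists the reference results. Tracing it takes listings, however. The TP and FP summaries carry no warning, and the level-of-evidence split in SAP 9.14.3.2 covers CDR, PPV and DR, not PSA.

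**Conclusion.** The dependence holds and follows from the definitions alone. Total PSA change in TP versus FP men is partly built in or due to treatment, and the cut-off in SAP 7.6 covers neither total PSA nor therapies other than radiation.

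It is a minor point. It is confined to an exploratory table, lies mainly in TP versus FP, and changes no primary or secondary result. Its size cannot be determined: every magnitude above rests on assumed rates of focal therapy and PSA response. The documents do not support reading the illustrations as the expected bias, or concluding that any observed TP versus FP difference would be wholly artefact.

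**What to change.** Keep the planned summaries in SAP 9.14.3.6 and add the following:

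1. For the TP, FP and TN subgroups, a second version of the total PSA summary that uses only values before the start of any radiation or other salvage focal therapy, with its n.
2. In SAP 7.6, the same cut-off for velocity and doubling time after other salvage focal therapy.
3. The number of men treated in each subgroup, and the number who are TP with no TP region (PSA response only).
4. A footnote that the planned version is not independent of the classification.

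A separate exclusion of Level 3 men is not needed once post-therapy values are removed, and it would break the match with the primary-analysis TP group.

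The cost is a short SAP amendment, one data filter and one extra table panel. The downside is that a man treated between Visit 4 (Day 7) and the next scheduled PSA at Day 90 may have no pre-therapy follow-up value and so not contribute to the added version. This is why that version should sit beside the planned one and not replace it. SAP 1.0 allows an amendment before database lock. After lock, the footnote and a note in the clinical study report would still serve.
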